# **SUMMARY OF CHANGES**

	Change	Section Affected	Summary of Change(s)
1.	Number of subjects increased from up to 15, to 25.	Section 4.1 Section 5.1 Section 14.2	Number of subjects increased to account for additional subjects enrolled onto INDV-6000-403 study.
2.	Concomitant medications or indications for such, will not be coded or summarized.	Section 13.1 Section 14.4.3	Concomitant medications are required to be listed only for this study.
3.	Detox and MOUD history will be collected and summarized.	Section 4.1 Section 4,2 Section 8.1 Section 14.4.3	This will be collected retrospectively for subjects enrolled in the study at the time of this amendment.
4.	Added that the safety population will be the primary population for all analyses.	Section 14.3	The safety population was defined but utilization for analyses not stated.
5.	Typographical error corrected.	Section 4.2	Injection 3 Visit, corrected to "Visit 3"
6.	Typographical error corrected.	Section 9.8	Subjects do not "check-in" to the clinic on day 1, therefore text updated to state subjects abstain from alcohol throughout the study.

### **STUDY SUMMARY**

Protocol Number: INDV-6000-404

Title:

An Open-label, treatment extension study for the Rapid Initiation of

Extended-Release Buprenorphine Subcutaneous Injection

(SUBLOCADE™)

**Rationale:** 

This study (INDV-6000-404) is to provide ongoing treatment with SUBLOCADE for up to 5 additional injections and safety monitoring for subjects who initiated SUBLOCADE following a single dose of transmucosal (TM) buprenorphine in study INDV-6000-403.

Target Population:

Subjects with moderate or severe opioid use disorder (OUD) who are seeking medication for OUD (MOUD) and have completed INDV-6000-

403 study.

Number of Subjects:

Up to 25 adult subjects

**Objective:** 

The objective of this study is to assess the longer-term safety of an abbreviated initiation protocol of SUBLOCADE in subjects who have completed INDV-6000-403. It is also to provide treatment to these individuals while they seek longer-term care arrangements, as it (on average) takes an individual with OUD 6 months between seeking treatment and achieving an appointment at a provider within the US.

**Study Design:** 

Only subjects who have completed the End of Treatment (EOT) procedures for Study INDV-6000-403, have signed the INDV-6000-404 informed consent form (ICF), and meet all the enrollment criteria may be considered for inclusion in this study.

The INDV-6000-403 EOT visit is 28 days after the subject's first dose of SUBLOCADE in INDV-6000-403, therefore the INDV-6000-403 EOT and the INDV-6000-404 screening and Day 1 visit for this study will occur within 2 days, thus the INDV-6000-403 EOT assessments will serve as the screening assessments for the Screening Visit (Day 1) of this study.

Any AEs and concomitant medications ongoing at the INDV-6000-403 EOT will be re-recorded for this study. In addition, demographics, height, medical/psychiatric, substance and drug of abuse history will not be recollected and will be taken from the INDV-6000-403 screening assessments. A detailed detox and MOUD treatment history will be collected at screening. For those subjects who have enrolled in the study prior to approval of protocol amendment 1, their detox and MOUD treatment history will be collected retrospectively at their next visit.

On Day 1, eligible subjects will receive a SC injection of 300mg SUBLOCADE. Before departing the site, any new adverse events (AEs) or concomitant medications will be recorded.

Subjects will return to the site for monthly injection visits every 4 weeks (-2 / +7 days) for a total of up to 5 injections. At Injection Visits 2 through 5, subjects will be evaluated in accordance with local standard of care and results for the following procedures will be recorded: urine pregnancy test (to be performed before SUBLOCADE administration for all female subjects who are of childbearing potential); urine drug screen (UDS) and evaluation of previous injection site for potential reaction and evidence of attempts to remove the depot. For injections 2 to 5, subjects may receive either a dose of 100 mg SUBLOCADE or 300 mg SUBLOCADE, based on the medical judgment of the Investigator, per the SUBLOCADE USPI. During each visit the subject will be assessed for AEs and use of concomitant medications.

All subjects will receive counselling as determined by local standard of care throughout the study from Day 1 through EOT.

All subjects who receive SUBLOCADE (including those who wish to discontinue early), will be encouraged to attend the EOT/ET visit 4 weeks after SUBLOCADE administration.

At the EOT/ET Visit, results for the following procedures and assessments will be recorded: urine pregnancy test for all female subjects who are of childbearing potential; evaluation of previous injection site for potential reaction and evidence of attempts to remove the depot; UDS; use of concomitant medications and assessment for AEs. At every Visit options for continued care should be discussed with the subject.

Any subject with ongoing AEs or concomitant medications at the EOT Visit will also be followed up by telephone 4 weeks later for a safety follow up to assess the ongoing AEs or concomitant medications only.

**Primary** The proportion of subjects with treatment emergent adverse events (TEAEs)

**Endpoint:** at any time during the treatment period.

Other Safety Additional safety endpoints will include assessment of: drug-related TEAEs, serious TEAEs, drug-related serious TEAEs, TEAEs leading to

treatment discontinuation and concomitant medications.

# LIST OF ABBREVIATIONS

AE adverse event

ALT alanine aminotransferase

BMI body mass index

CRF case report form

EOT end of treatment

GCP Good Clinical Practice

GMP Good Manufacturing Practice

ICF informed consent form

ICH International Council for Harmonisation of Technical Requirements for

Pharmaceuticals for Human Use

IRB Institutional Review Board

MedDRA Medical Dictionary for Regulatory Activities

mg Milligram

MAOI monoamine oxidase inhibitor

MOUD Medication for Opioid Use disorder

NNRTI non-nucleoside reverse transcriptase inhibitor

NMP N-methyl-2-pyrrolidone

OUD opioid use disorder

PLGH poly(DL-lactide-co-glycolide) with a carboxylic acid end group

QA quality assurance

SAE serious adverse event

SAP statistical analysis plan

SC subcutaneous(ly)

SD standard deviation

SOP standard operating procedure

SUSAR suspected unexpected serious adverse reaction

TEAE treatment-emergent adverse event

TM Transmucosal

UDS urine drug screen

ULN upper limit of normal

USPI United States Prescribing Information

WHO World Health Organization

# 1 INTRODUCTION AND RATIONALE

# 1.1 Background

Opioid use disorder (OUD) is a neurobehavioral syndrome characterised by repeated, compulsive seeking or use of an opioid despite adverse social, psychological and physical consequences (SAMHSA 2004). This chronic, relapsing disease has grown to epidemic proportions. The clinical course of OUD typically includes periods of exacerbation and remission, but the patient is never disease-free. Medications for OUD (MOUD) are recommended by treatment guidelines as the current standard of care for OUD (Kampman 2015), combined with counselling/behavioural therapy to provide a whole-patient approach to the treatment of OUD.

SUBLOCADETM (extended-release buprenorphine) injection, for subcutaneous (SC) use (CIII) is an extended-release formulation of buprenorphine, a mu-opioid receptor partial agonist. SUBLOCADE is administered once monthly by SC injection and provides sustained plasma levels of buprenorphine over the dosing interval. SUBLOCADE uses buprenorphine and the ATRIGEL® Delivery System, which consists of a biodegradable polymer poly (DL-lactide-co-glycolide) with a carboxylic acid end group (PLGH), dissolved in a biocompatible solvent, N-methyl-2-pyrrolidone (NMP). SUBLOCADE is injected as a solution, and subsequent precipitation of the polymer creates a solid depot containing buprenorphine. After initial formation of the depot, buprenorphine is released via diffusion from, and the biodegradation of, the depot.

See SUBLOCADE USPI for further information.

#### 1.2 Study Rationale

Currently, patients who are appropriate candidates for SUBLOCADE must initiate treatment with transmucosal (TM) buprenorphine for a minimum of 7 days before receiving their first injection

(SUBLOCADE United States Prescribing Information [USPI]). Study INDV-6000-403 is being conducted to evaluate the safety and tolerability of starting SUBLOCADE treatment following a shorter period of TM buprenorphine treatment. This study (INDV-6000-404) is to provide ongoing treatment with SUBLOCADE for up to 5 additional injections and safety monitoring for subjects who initiated SUBLOCADE following a single dose of transmucosal (TM) buprenorphine in study INDV-6000-403.

#### 1.2.1 Dosing Regimen

SUBLOCADE should be administered as per the instructions for use in the SUBLOCADE USPI.

The recommended initial dose of SUBLOCADE is 300mg monthly for the first 2 injections of treatment. Subjects have received 1 x 300mg SUBLOCADE injection in the

INDV-6000-403 study, therefore subjects must receive 300mg SUBLOCADE for the first injection of this study. Subjects may receive either 100 mg or 300 mg SUBLOCADE for the maintenance dose (all subsequent injections), based on the medical judgment of the Investigator as per the SUBLOCADE USPI.

#### 1.3 Risk-Benefit Assessment

Buprenorphine is a partial agonist at the mu-opioid receptor. As such, it produces a submaximal pharmacological response compared with that of a full agonist at these receptors and provides a greater margin of safety with respect to respiratory depression compared with full agonists. Buprenorphine has been shown to be an efficacious and safe treatment for OUD when used as directed. For this extension study, SUBLOCADE will be administered as recommended in the SUBLOCADE USPI.

#### 1.3.1 Risk Assessment

The safety profile of buprenorphine is well-established, and the AE profile of buprenorphine is well characterised. Commonly reported treatment-emergent AEs include drug withdrawal syndrome, constipation, headache, nausea and vomiting. Buprenorphine has been approved for multiple indications and routes of administration (e.g., TM, buccal, intramuscular, intravenous, transdermal, rectal and subcutaneous) in multiple countries and by various manufacturers. Buprenorphine extended-release SC injection was approved as a monthly treatment for OUD in 2017 (SUBLOCADE USPI).

The most common adverse drug reactions with SUBLOCADE were constipation, nausea, hepatic enzyme increased, headache, injection site pain, injection site pruritus, vomiting and fatigue. Injection site reactions were generally mild to moderate in severity, none were serious, and they decreased in frequency with subsequent injections. There were no unexpected safety findings. The safety profile of SUBLOCADE observed in the Phase III studies was generally consistent with the known safety profile of buprenorphine, with the expected exception of injection site tolerability and reaction.

#### 1.3.2 Benefit Assessment

Clear efficacy was demonstrated both in the pivotal and in additional supporting studies of the SUBLOCADE clinical development programme (SUBLOCADE USPI). While subjects will receive limited benefit from participation in the single-dose (of SUBLOCADE) study (INDV-6000-403), participation in the combined INDV-6000-403 and INDV-6000-404 studies will allow more meaningful engagement with MOUD and the results could provide support for more rapid SUBLOCADE initiation, which is expected to improve treatment compliance, engagement and retention in treatment. With increasing amounts of fentanyl contamination of the heroin drug supply, it is also important to treat patients with a medicine that can protect them from overdose as soon as they are willing to engage in treatment. Recently reported data (Wiest 2019) supports that buprenorphine, administered at doses resulting in consistent plasma levels of 2ng/mL

and 5ng/mL (similar to the concentrations resulting from both labelled doses of SUBLOCADE), is able to dose dependently inhibit fentanyl-induced respiratory depression. Being able to initiate treatment-seeking patients with SUBLOCADE on the 1st day of treatment may therefore help to protect patients when they are most vulnerable.

## 1.3.3 Overall Risk-Benefit Summary

Taken together, these findings indicate a favourable benefit/risk assessment for this extension of the single dose study (INDV-6000-403) to evaluate a more rapid treatment initiation protocol for SUBLOCADE in patients with OUD.

# 2 STUDY OBJECTIVE

The objective of this study is to assess the longer-term safety of an abbreviated initiation protocol of SUBLOCADE in subjects who have completed INDV-6000-403. It is also to provide treatment to these individuals while they seek longer-term care arrangements, as it (on average) takes an individual with OUD 6 months between seeking treatment and achieving an appointment at a provider within the US.

# 3 STUDY ENDPOINTS

# 3.1 Primary

The proportion of subjects with treatment emergent adverse events (TEAEs) at any time during the treatment period (i.e., any time after administration of SUBLOCADE).

# 3.2 Other Safety Assessments

Additional safety endpoints will include assessment of: drug-related TEAEs, serious TEAEs, drug-related serious TEAEs, TEAEs leading to treatment discontinuation and concomitant medications.

# 4 STUDY PLAN

# 4.1 Study Design

This is a single center, open-label, SUBLOCADE treatment extension study in which up to 25 subjects diagnosed with moderate or severe OUD will be enrolled. A subject is defined as enrolled when the first dose of SUBLOCADE is administered for this study.

Only subjects who have completed the End of Treatment (EOT) procedures for Study INDV-6000-403, have signed the INDV-6000-404 informed consent form (ICF), and meet all the enrollment criteria may be considered for inclusion in this study.

The INDV-6000-403 EOT visit is 28 days after the subjects first dose of SUBLOCADE in INDV-6000-403, therefore the INDV-6000-403 EOT and the INDV-6000-404 screening and Day 1 visit for this study will occur within 2 days.

The ICF may be shared with the potential subject before the INDV-6000-403 EOT Visit to discuss this study as a possible treatment option. However, the ICF must not be signed until all assessments for the INDV-6000-403 EOT Visit are complete.

The INDV-6000-403 EOT assessments will serve as the screening assessments for the Screening Visit (Day 1) of this study. Any AEs and concomitant medications ongoing at the INDV-6000-403 EOT will be re-recorded for this study. In addition, demographics, height, medical/psychiatric, substance and drug of abuse history will not be re-collected and will be taken from the INDV-6000-403 screening assessments. A detailed detox and MOUD treatment history will be collected at screening. For those subjects who have enrolled in the study prior to approval of protocol amendment 1, their detox and MOUD treatment history will be collected retrospectively at their next visit.

On Day 1, eligible subjects will receive a SC injection of 300mg SUBLOCADE. Before departing the site, any new adverse events (AEs) or concomitant medications will be recorded.

Subjects will return to the site for monthly injection visits every 4 weeks (-2 / +7 days) for a total of up to 5 injections. At Injection Visits 2 through 5, subjects will be evaluated in accordance with local standard of care and results for the following procedures will be recorded: urine pregnancy test (to be performed before SUBLOCADE administration for all female subjects who are of childbearing potential); urine drug screen (UDS) and evaluation of previous injection site for potential reaction and evidence of attempts to remove the depot. For injections 2 to 5, subjects may receive either a dose of 100 mg SUBLOCADE or 300 mg SUBLOCADE, based on the medical judgment of the Investigator, per the SUBLOCADE USPI. During each visit the subject will be assessed for AEs and use of concomitant medications.

All subjects will receive counselling as determined by local standard of care throughout the study from Day 1 through EOT.

All subjects who receive SUBLOCADE (including those who wish to discontinue early), will be encouraged to attend the EOT/ET visit 4 weeks after SUBLOCADE administration.

At the EOT/ET Visit, results for the following procedures and assessments will be recorded: urine pregnancy test for all female subjects who are of childbearing potential; evaluation of previous injection site for potential reaction and evidence of attempts to remove the depot; UDS; use of concomitant medications and assessment for AEs. At every Visit options for continued care should be discussed with the subject.

Any subject with ongoing AEs or concomitant medications at the EOT Visit will also be followed up by telephone 4 weeks later for a safety follow up to assess the ongoing AEs or concomitant medications only.

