#### 4.2 Schedule of Assessments

An overview of the schedule of assessments for the study is provided in Table 1.

Table 1 Schedule of Assessments – Overview of Study

Procedure/Assessment	Screening	Injection 1	Injection 2	Injection 3	Injection 4	Injection 5	ET / EOT 	Safety Follow up 
Visit Number	3	1	2	3	4	5	6	7
Day(s)		1	29	57	85	113	141	169
Window (days)		+2	-2 / +7	-2 / +7	-2 / +7	-2 / +7	-2 / +7	-7 / +7
Informed Consent 	X							
Inclusion/Exclusion Criteria	X			2				
Demographics 	403 							
Medical/Psychiatric History 	403 			3.				
Substance/Drug Use History 	403 							
Height 	403 							
Weight/BMI 	403 EOT 							
Urine Pregnancy Test 	403 EOT 		X	X	X	X	X	
UDS 	403 EOT 		X	X	X	X	X	
Injection Site Evaluation 	403 EOT 		X	X	X	X	X	
AE Assessment	X 		X	X	X	X	X	
Concomitant Medications	X 		X	X	X	X	X	X
Study Drug Administration		X	X	X	X	X		
MOUD and treatment History 	X							
Counselling 	2			X	ı	1		3.

AE=adverse event; BMI=body mass index; EOT=End-of-Treatment; ET=Early Termination; OUD=opioid use disorder; UDS=urine drug screen; MOUD=medication for opioid use disorder

Written informed consent must be obtained after completion of all INDV-6000-403 EOT procedures and before any INDV-6000-404 study-specific assessments/procedures are initiated.

2. This data will not be re-collected; the data from the INDV-6000-403 screening visit will be used.

- 3. This data will not be re-collected; the data from the INDV-6000-403 EOT visit will be used.
- 4. Any ongoing (at the INDV-6000-403 EOT) or new AEs or concomitant medications in this study will be recorded.
- 5. Required for female subjects of childbearing potential only, to be performed before SUBLOCADE dosing at Visits 1 to 6.
- 6. Qualitative test to be performed before SUBLOCADE dosing at Visits 1 to 6.
- 7. Injection site will be evaluated for signs of attempted removal before SUBLOCADE dosing at Visits 1 to 6. Any injection site reactions or infections will be recorded as AEs.
- 8. All subjects will receive counselling as determined by local standard of care throughout the study from Day 1 through EOT.

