- 9. All subjects who receive SUBLOCADE (including those who wish to discontinue early), will be encouraged to attend the EOT visit 4 weeks after SUBLOCADE administration.
- 10. Any subject with ongoing AEs or concomitant medications at the EOT/ET Visit will also be followed up by telephone 4 weeks later for a safety follow up to assess the ongoing AEs or concomitant medications only.
- 11. A detailed detox and MOUD treatment history will be collected at screening. For those subjects who have enrolled in the study prior to approval of protocol amendment 1, their detox and MOUD treatment history will be collected retrospectively at their next visit.

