#### 9.4 Dose and Administration

SUBLOCADE will be supplied by the Sponsor as a single, pre-filled syringe, the entire contents of which should be administered during a single SC injection by a licensed healthcare provider as delegated by the Investigator.

SUBLOCADE should be administered as per the instructions for use in the SUBLOCADE USPI. The recommended initial dose of SUBLOCADE is 300mg monthly for the first 2 injections of treatment. Subjects have received 1 x 300mg SUBLOCADE injection in the INDV-6000-403 study, therefore subjects must receive 300mg SUBLOCADE for the first injection of this study.

Subjects may receive either 100 mg or 300 mg SUBLOCADE for the maintenance dose (all subsequent injections), based on the medical judgment of the Investigator as per the SUBLOCADE USPI. Reasons for dose adjustments should be recorded in the source and CRF.

Time of dose for SUBLOCADE is defined as the time the SC injection is complete. The time of dose and any dosing observations (e.g., partial doses or other issues with the injection) will be recorded in the source documentation; in addition, time of dose will be recorded in the CRF.

The Investigator will not supply SUBLOCADE to any person except study personnel for SC injection of subjects in this study. SUBLOCADE will be dispensed under the supervision of the Investigator, a suitably qualified member of the study team, or by a pharmacist. The Investigator or designee agrees to neither administer SUBLOCADE from, nor store it at any location other than the study clinic agreed upon with the Sponsor. Clinic personnel must maintain accountability records per the Pharmacy Manual.

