2 STATISTICAL HYPOTHESES

For this single arm study, the analysis methods are descriptive. Therefore, statistical testing and hypotheses are not applicable.

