5.1.5 General Conventions for Analysis

Continuous variables will be summarised using the descriptive statistics mean, standard deviations (SD), median, minimum and maximum, unless other statistics are specified. Categorical variables will be reported as frequency counts (including number missing) and the percentage of subjects in corresponding categories.

Individual subject data will be presented by subject in data listings. Data listings will include all data collected from the initial screening visit to the Safety follow-up visit (including unscheduled visits).

The derivation of Study Day will be made relative to the date/time of the first administration of SUBLOCADE in this study.

Observed data is used for analysis, unless handling of missing data is described otherwise within the analysis description or in Section 6.5.

If there are ≤ 6 AEs reported, only a listing and no AE summary tables will be produced, except for the table of AE occurrences used for public disclosure. The table of AE occurrences for public disclosure will only be produced if there are ≥ 1 AEs reported.

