6.3 Appendix 3: Definition and Use of Visits and Visit Windows in Reporting

Nominal visits will be used for the analysis without regard to visit windows. The nominal visits will be labelled in TLFs as Injection 1 – Injection 5 and ET/EOT.

Unscheduled visits will be given an analysis visit number in sequential order according to chronological date/time following the most recent scheduled visit.

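### Do Protocol Section 4.1 and Table 1 contradict each other on how far apart the injections may fall?

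*Protocol*

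**What the plan says.** Protocol Section 4.1 (repeated in the Study Summary and in SAP Section 1.3) schedules "monthly injection visits every 4 weeks (-2 / +7 days) for a total of up to 5 injections". It does not say whether the tolerance is counted from the previous injection or from Day 1.

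Table 1 in Protocol Section 4.2 (repeated as SAP Table 3) places Injection 1 on Day 1 with a +2 window. Injections 2 to 5, EOT and the safety call are on Days "29 57 85 113 141 169". The window is -2 / +7 for Injections 2 to 5 and for EOT. Footnote 9, attached to the EOT column, says that subjects "will be encouraged to attend the EOT visit 4 weeks after SUBLOCADE administration".

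Protocol Section 9.4 describes dosing as monthly ("The recommended initial dose of SUBLOCADE is 300mg monthly for the first 2 injections of treatment") and refers to the prescribing information. No section gives a minimum number of days between injections.

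On the analysis side, SAP Section 5.1.5 states: "The derivation of Study Day will be made relative to the date/time of the first administration of SUBLOCADE in this study". SAP Section 6.3 states: "Nominal visits will be used for the analysis without regard to visit windows". SAP Section 2 adds: "For this single arm study, the analysis methods are descriptive".

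**The concern.** The word *every* suggests spacing between visits. Taken that way, Section 4.1 allows no interval shorter than 26 days. Table 1 appears to tie each visit to a fixed study day, so a late visit followed by an early one can both be in window and only 19 days apart. For a monthly depot injection that is a noticeable compression.

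If the two places did set different rules, sites could dose closer together than the text intends without logging a deviation, or log deviations for visits the text allows. Adverse events are collected only up to EOT, and the follow-up call covers only events already ongoing. A short gap between Injection 5 and EOT would therefore also cut the time in which new events can be observed. Because visits are analysed under their nominal labels, the summary tables would not show any of this.

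**Working it through.** **Inputs.** Scheduled days 1, 29, 57, 85, 113 and 141, and windows of +2 (Injection 1) and -2 / +7 (Injections 2 to 5 and EOT), from Protocol Table 1. Interval of 4 weeks with -2 / +7, from Protocol Section 4.1. Origin of study day, from SAP Section 5.1.5.

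**Step 1: the nominal schedule.** 29 - 1 = 57 - 29 = 85 - 57 = 113 - 85 = 141 - 113 = 28 days. Text and table agree on the 4-week step.

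**Step 2: both places read as fixed study days.**
- Smallest gap, Injection 2 to 3: (57 - 2) - (29 + 7) = 55 - 36 = 19 days.
- Largest gap, Injection 2 to 3: (57 + 7) - (29 - 2) = 64 - 27 = 37 days.
- Injections 3 to 4 and 4 to 5 give the same range, because the spacing and windows are the same.

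**Step 3: both places read as an interval from the previous injection.** 28 - 2 = 26 days to 28 + 7 = 35 days. The shortest gap in step 2 is (26 - 19) / 26 = 27% below this minimum.

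**Step 4: one place read each way.** Chaining the interval rule from Day 1 gives 1 + 26k to 1 + 35k for the k-th injection after the first:

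| Injection | Chained intervals | Table 1 window |
|---|---|---|
| 2 | Day 27 to 36 | Day 27 to 36 |
| 3 | Day 53 to 71 | Day 55 to 64 |
| 4 | Day 79 to 106 | Day 83 to 92 |
| 5 | Day 105 to 141 | Day 111 to 120 |

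The ranges differ from Injection 3 onward, but only because the text is taken as an interval and the table as fixed days.

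**Step 5: Injection 1 to 2.** Counting the +2 window of Injection 1 as a delay against a fixed calendar would give (29 - 2) - (1 + 2) = 24 days. That count is not right. Protocol Section 6.4 starts the treatment period with the injection on Day 1, and SAP Section 5.1.5 counts study days from that dose. Using the +2 therefore moves Day 1 itself. The gap is 27 - 1 = 26 to 36 - 1 = 35 days on either reading.

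**Step 6: Injection 5 to EOT.** Day numbers alone give (141 - 2) - (113 + 7) = 19 to (141 + 7) - (113 - 2) = 37 days. Footnote 9, however, ties this visit to the dose. In-window Injection 5 falls on Days 111 to 120. Adding 28 gives Days 139 to 148. Table 1's EOT window is 141 - 2 = 139 to 141 + 7 = 148. The two match exactly, so a site can meet the footnote and the window together whatever the date of Injection 5.

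**Step 7: where windows enter the analysis.**
- The primary endpoint is any treatment-emergent event over the whole treatment period (Protocol Section 3.1, SAP Section 5.3.2). It has no visit window in it.
- Urine drug screens are summarised by visit, and dose strength by injection number (SAP Sections 5.5.7 and 5.5.2), both under nominal labels.
- Protocol deviations are listed, and important ones affect neither the analyses nor the populations (SAP Section 6.4).
- Time of dose is recorded in the CRF (Protocol Section 9.4) and exposure data are listed (SAP Section 5.5.2), so actual intervals can be recovered.

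**The case for a change.** The strongest case for a change has three parts.

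First, spacing is the natural sense of Section 4.1, and a 19-day gap sits badly with a product described throughout as monthly. It stands that the anchor is not written down, and that one visit could be classed as compliant or as a deviation depending on the reading. That is missing detail rather than two rules in conflict. Section 8 of the protocol says that timing is summarised in Table 1, so text and table are meant to describe one schedule. The figure of 26 to 35 days appears nowhere in the documents. Nor is Table 1 the only rule on dosing: administration must also follow the prescribing information. Whether that source limits the interval cannot be seen from these documents, so one cannot say that sites are free to dose 19 days apart.

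Second, EOT closes the collection of new adverse events, so the gap after Injection 5 bears on the primary endpoint. A site that scheduled EOT on Table 1's day numbers alone after a late Injection 5 could observe 19 days instead of 28, which is (28 - 19) / 28 = 32% less. That requires setting aside the footnote attached to that very column. With the footnote applied, the loss disappears.

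Third, summaries by nominal visit would hide irregular spacing. That is true of the summaries. It is not true of the data, since dose times are recorded and exposure is listed.

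**Conclusion.** There is no contradiction and no arithmetic error. The protocol leaves unstated whether the -2 / +7 tolerance runs from Day 1 or from the previous injection. The two readings give 19 to 37 days against 26 to 35 days for Injections 2 to 3, 3 to 4 and 4 to 5. They do not differ for Injection 1 to 2, and the EOT window agrees exactly with four weeks after any in-window Injection 5.

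The consequence is confined to how an off-schedule visit is labelled in the deviation listing. No estimate, population or endpoint definition depends on that label, in a descriptive single-arm study of at most 25 subjects. Stating the anchor would only write the detail down; if it were Day 1, Table 1 would stay as it is. Which anchor and limits apply is a clinical decision for the sponsor and is not judged here.

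This conclusion rests on two assumptions: that the EOT column is read together with its footnote, and that dose times are recorded as Protocol Section 9.4 requires.
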